13.9.6 Analysis of the Exploratory Endpoints

- Clinical response by assessing disease activity using: 28-Tender and Swollen Joint Counts and Joint Pain VAS will be analyzed using a t-test
- Number of SLE flares will be analyzed using frequency table methods
- Time to first SLE flare in patients will be analyzed using life-table methods
- Proportion of patients with an increase or addition in lupus therapy will be analyzed using frequency table methods

- Proportion of treatment failure will be analyzed using frequency table methods. Patients will be considered as treatment failure if they receive more than 5 mg prednisone equivalent/day at any time between Week 24 (Visit 9) and Week 36 (Visit 12) or if their CS dose is increased above the Week 24 level or if any increase of immunosuppressive treatment between Week 12 and Week 36 above CS dose at Week 12 is recorded.
- Changes in the SF-36 score: Physical Component Summary (PCS) and Mental Component Summary (MCS) scores using non-parametric Wilcoxon-test; if one is statistically significant then the individual domain scores will also be analyzed. Also clinically meaningful improvements \geq Minimum Clinically Important Differences (MCID) of 2.5 points for summary and 5.0 points for domain scores will be analyzed
- Quality of life using FACIT fatigue score will be analyzed using a t-test
- Changes in the levels of auto-antibodies (anti-dsDNA, anti-Smith antigen [anti-Sm], anti-RNP, anti-SSA/Ro, anti-SSB/La, anti-cardiolipin, and anti- β 2-glycoprotein I antibodies) will be analyzed using a t-test
- Changes in the levels of biomarkers (C3, C4, CH50) will be analyzed versus baseline
- Anti-IFN α and anti-KLH antibody isotyping
- Anti-Hemagglutinin antibody response: seroconversion (four fold increase in antibody titers post-vaccination) and seroprotection (HIA antibody titers \geq 1:40 post-vaccination)
- Correlation between immunogenicity responses and clinical or biological parameters will be performed on an exploratory basis

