2.2.3 Exploratory objectives

The exploratory objectives of this study are:

- To assess disease activity using:
 - The Physician Global Assessment (PGA) score
 - The 28-Tender and Swollen joint counts
 - A Joint Pain Visual Analog Scale (VAS)
 - The flare description
 - The changes in Lupus therapy
- To assess quality-of-life using:
 - The Short Form-36 (SF-36) questionnaire
 - The Functional Assessment of Chronic Illness Therapy (FACIT) fatigue score.
- To assess biological parameters:
 - Levels of lupus-related serum auto-antibodies and biomarkers
 - Neutralizing Anti-IFN α antibodies towards IFN α subtypes
 - Anti-IFN α and anti-KLH antibody isotyping
 - IFN β cross neutralization
 - Antibody response to influenza vaccination
- To assess correlations between immune responses, IFN gene signature and clinical responses

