5.2.4.2 Sensitivity and supplementary analyses

The primary efficacy analysis will be repeated on the PP set as a supplementary analysis (Statistical tables 14.2.2.1.1 to 14.2.2.2.1).

It will be also repeated on the FAS population excluding patients with unblinding issue (see section 5.3.6) (Statistical tables 14.2.3.1.1 to 14.2.3.1.3 & 14.2.3.2.1 to 14.2.3.2.2.).

Then, the primary efficacy analysis will be repeated on the FAS for patients IFN-K treated with status of IFN α neutralizing antibodies (positive/negative) at Week 36 as dependent variable.

(Statistical tables 14.2.3.3.1 & 14.2.3.3.2).

Finally, the following analysis will be presented as a sensitivity analysis.

The time variation in IFN gene signature (first co-primary endpoint) will be modelled using a MMRM (mixed model for repeated measures) with random intercept, with percent change at each time point as dependent variable, and minimization factors used for randomization (Ethnic origin (see section 9 Derived data), Age group, Presence or absence of renal involvement according to BILAG at screening, corticosteroid treatment, hydroxychloroquine treatment and MMF treatment at screening, treatment and time as explanatory variables.

The treatment by time interaction will also be included in the model. (Statistical table 14.2.4).

Linearity will be checked graphically. In case of absence of evidence of non-linearity, time will be treated as continuous (variable calculated as the actual number of days since baseline). Otherwise, it will be treated as categorical. (Statistical figure 14.2.1)

Statistical Analysis Plan

Study Name: IFN-K-002

SAP version & date: v4, 18/Jun/2018

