5.2.4.4 Immunogenicity analysis

The following analysis will be performed on the PP population.

5.2.4.4.1 *Anti-IFN α binding antibody titers.*

- The number of patients with a positive antibody response over time (seropositivity) will be analyzed using frequency table methods (Statistical table 14.2.19). The definitions are the followings:
 - Seropositivity: A positive result (seropositivity) is defined when titer was ≥ 400 dil-1 and a negative result when titer is < 400 dil-1.
- Descriptive analysis will be done on Log-transformed dilution titers for anti-IFN α binding antibodies expressed as dilution factors at each time point. (Statistical table 14.2.20)
- Reverse cumulative distribution curves will be generated using anti-IFN α antibody titers (Statistical figure 14.2.2)
- GMT for anti-IFN α binding antibodies will be presented. Results will be expressed with 95% CI (Statistical table 14.2.21).

All corresponding data will be listed in Listing 16.2.6.7.

5.2.4.4.2 *Anti-IFN α antibody neutralizing capacity (NC50).*

- The number of patients with a positive antibody response over time (seropositivity) will be analyzed using frequency table methods (Statistical table 14.2.22). The definitions are the followings:
 - Seropositivity: A positive result (seropositivity) is defined when NC50 was ≥ 200 dil-1 and a negative result when NC50 is < 200 dil-1.
- Descriptive analysis will be done on Log-transformed NC50 for anti-IFN α neutralizing antibodies expressed as dilution factors at each time point (Statistical table 14.2.23)
- Reverse cumulative distribution curves will be generated using NC50 (Statistical figure 14.2.3)
- GMT for anti-IFN α neutralizing antibodies will be presented. Results will be expressed with 95% CI (Statistical table 14.2.24).

All corresponding data will be listed in Listing 16.2.6.8.

5.2.4.4.3 *Anti-KLH binding antibody titers.*

- The number of patients with a positive antibody response over time (seropositivity) will be analyzed using frequency table methods (Statistical table 14.2.25). The definitions are the followings:

Statistical Analysis Plan

Study Name: IFN-K-002

SAP version & date: v4, 18/Jun/2018

- Seropositivity: A positive result (seropositivity) is defined when titer was ≥ 400 dil-1 and a negative result when titer is <400 dil-1.
- Descriptive analysis will be done on Log-transformed dilution titers for anti-KLH binding antibodies expressed as dilution factors at each time (Statistical table 14.2.26)

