IFN β and IFN ω cross neutralization data will be provided in Listing 16.2.6.20

5.2.4.5.13 ***Correlation***

Correlation between immunogenicity responses (Anti-IFN α binding positive / neutralizing antibodies positive vs anti-IFN α binding positive / neutralizing antibodies negative) and clinical parameters (BICLA & SRI-4); between clinical and biological parameters (IFN gene signature, C3, dsDNA, ANA), and between immunogenicity responses and biological parameters will be presented on the PP population. The following analyses will be performed:

- Qualitative description for clinical parameters at V12 by status (positive/negative) of anti IFN α neutralizing antibodies at V12 on patients treated with IFN-K and with positive anti IFN α binding antibodies at V12
- Quantitative or qualitative description for biological parameters at V12 by treatment group on patients responder for BICLA at V12
- Quantitative or qualitative description for biological parameters at V12 by treatment group on patients non responder for BICLA at V12
- Quantitative or qualitative description for biological parameters at V12 by treatment group on patients responder for SRI4 at V12
- Quantitative or qualitative description for biological parameters at V12 by treatment group on patients non responder for SRI4 at V12
- Quantitative or qualitative description for biological parameters at V12 by status (positive/negative) of anti IFN α neutralizing antibodies at V12 on patients treated with IFN-K and with positive anti IFN α binding antibodies at V12

(Statistical Tables 14.2.45.1 to 14.2.45.6)

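### SAP 5.2.4.5.13 (Correlation) plans no measure of association, so antibody dose-response and the signature–clinical, C3 and anti-dsDNA links are not estimated

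*SAP*

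**What the plan says.** SAP 2.2.3 sets the objective: "To assess correlations between immune responses, IFN gene signature and clinical responses". Protocol 13.9.6 commits to part of it without naming a method: "Correlation between immunogenicity responses and clinical or biological parameters will be performed on an exploratory basis".

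SAP 5.2.4.5.13 carries this out on the per-protocol set with six tables:

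- Two tables cover IFN-K patients with positive binding antibodies at Visit 12 (Week 36). One begins "Qualitative description for clinical parameters at V12 by status (positive/negative) of anti"; the other does the same for biological parameters.
- Four tables describe biological parameters by arm within response groups. For BICLA these are "Quantitative or qualitative description for biological parameters at V12 by treatment group on patients responder for BICLA at V12" and "Quantitative or qualitative description for biological parameters at V12 by treatment group on patients non responder for BICLA at V12", and there is a matching pair for SRI-4.

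Positive neutralizing status, in SAP 5.2.4.4.2, "is defined when NC50 was ≥ 200 dil-1". The same subsection keeps the continuous measure: "Descriptive analysis will be done on Log-transformed NC50".

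Neutralizing status also appears in models outside this section. In SAP 5.2.4.2, "the primary efficacy analysis will be repeated on the FAS for patients IFN-K treated", with status brought into the model. SAP 5.2.4.3.1 does likewise for SRI-4 and composite SRI-4. SAP 5.2.4.5.2 fits a Cox model of time to first flare in IFN-K patients by presence or absence of neutralizing antibodies.

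**The concern.** A section headed Correlation, written to serve an objective about correlations, would be expected to estimate at least one. This one does not. It takes a continuous NC50 and uses only the side of the cut on which it falls. It also shows Week 36 values, which mix a patient's starting level with the response to treatment, although the SAP derives changes from baseline elsewhere.

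The gap touches the mechanistic question carried over from the first study. Protocol 5.4.3 reports that the fall in SLE-associated gene expression, and the rise in C3 from baseline, correlated with anti-IFNα antibody level. Protocol 5.1 says the trial aims to confirm the preliminary biological results. As planned, 5.2.4.5.13 could reproduce neither correlation. In addition, SAP 5.2.4.1 pairs signature neutralization with a BICLA trend as the success criterion, and 5.2.4.3.1 holds SRI-4 in reserve as a primary endpoint for later development. No planned analysis estimates whether signature change goes with either response.

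**Working it through.** **1. What is estimated, link by link**

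| Link | Where addressed | Form |
|---|---|---|
| Antibody – signature change | SAP 5.2.4.2 (ANCOVA) | status only |
| Antibody – BICLA | SAP 5.2.4.2 (logistic) | status only |
| Antibody – SRI-4 | SAP 5.2.4.3.1 (logistic) | status only |
| Antibody – flare | SAP 5.2.4.5.2 (Cox) | status only |
| Antibody – C3, anti-dsDNA | SAP 5.2.4.5.13 | description by status, Week 36 |
| Signature – BICLA, SRI-4 | SAP 5.2.4.5.13 | description, Week 36 |
| Signature – C3, anti-dsDNA | none | – |

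The continuous inputs already exist: log binding titre and log NC50 (5.2.4.4.1, 5.2.4.4.2), percent change in signature (5.2.4.1), and change in anti-dsDNA and C3 (5.2.4.5.7, 5.2.4.5.8).

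**2. Role of neutralizing status in the models**

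SAP 5.2.4.2, 5.2.4.3.1 and the matching titles in the table list (14.2.3.3.1, 14.2.3.3.2, 14.2.5.3, 14.2.5.8, 14.2.5.11) call status the dependent variable. The primary ANCOVA has percent change in signature as its outcome, and the logistic model has BICLA response. Restricting to IFN-K patients removes treatment as a factor, so status can only take treatment's place as an explanatory variable. The Cox model in 5.2.4.5.2 already uses it that way.

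**3. Cost of the split (illustration)**

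The documents give no figure for these analyses. The 80 evaluable patients per arm come from SAP 2.3.2. The correlation ρ and the share p who are neutralizing-positive are assumptions. Bivariate normality is assumed, with two-sided 5%.

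- Continuous level: power = Φ(atanh(ρ)·√(n − 3) − 1.96). With ρ = 0.3 and n = 80: 0.3095 × 8.775 − 1.96 = 0.756, so 78%.
- After a split, ρ is multiplied by f = φ(z_p)/√(p(1 − p)). This is 0.798 at p = 0.5, 0.700 at 0.8 and 0.585 at 0.9. Information kept is f²: 64%, 49% and 34%.
- At p = 0.9: ρ becomes 0.1755, and 0.1773 × 8.775 − 1.96 = −0.404, so 34%.

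| n | ρ | Continuous | 50:50 | 80:20 | 90:10 |
|---|---|---|---|---|---|
| 80 | 0.2 | 43% | 29% | 24% | 18% |
| 80 | 0.3 | 78% | 57% | 46% | 34% |
| 80 | 0.4 | 96% | 83% | 71% | 55% |
| 60 | 0.3 | 65% | 45% | 36% | 27% |

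A skewed split is plausible. Protocol 5.5 says that every patient in the 120 and 240 µg groups of the first study who had a fourth administration developed neutralizing antibodies, and SAP 3.3.2 excludes patients with fewer than four doses from the per-protocol set. At 90% positive, 0.10 × 80 = 8 patients would be negative. Those groups were small, and status at Week 36 may differ.

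**4. Size of the response groups**

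At the planned BICLA rates, responders number 0.406 × 80 ≈ 32 (IFN-K) and 0.206 × 80 ≈ 16 (placebo), leaving about 48 and 64 non-responders. A responder versus non-responder mean difference would have a 95% half-width of 1.96·√(1/32 + 1/48) = 0.45 SD in IFN-K and 1.96·√(1/16 + 1/64) = 0.55 SD in placebo. The SAP plans neither contrast.

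**The case against.** The strongest reply is that the section should not be read alone. The models in 5.2.4.2, 5.2.4.3.1 and 5.2.4.5.2 relate immune response to signature change, BICLA, SRI-4 and flare, and the signature model uses percent change from baseline. That stands. A reader might infer from 5.2.4.5.13 that the objective cannot be answered; the documents do not support that. Two of the three pairs in the objective are modelled, in binary form.

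Two other tempting readings also fail. One is that baseline differences swamp the effect at Week 36: the documents give no baseline variance or baseline-to-Week-36 correlation, so this cannot be shown. The other is that most of the antibody information is lost: at an even split 64% is kept, and log titres, GMTs and individual listings are reported in any case. Nor are all six tables confined to responders. Four are split by response, two of them in non-responders, so an informal comparison within each arm is possible.

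The protocol names no method and calls the work exploratory, leaving detail to the SAP. Nothing in the protocol is therefore contradicted by a choice of method, though a section with no association measure still falls short of the stated aim. It is also fair that regressing response on achieved titre conditions on a post-randomisation variable, as the existing subgroup tables do. That calls for a label and is no reason to omit the estimate.

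**Conclusion.** The point holds as a minor improvement. SAP 5.2.4.5.13 plans no association measure and uses only dichotomised antibody status and Week 36 values. Antibody dose-response, signature change against BICLA and SRI-4, and the C3 and anti-dsDNA links are left unestimated. The models elsewhere cover the antibody links in binary form only, and those in 5.2.4.2 and 5.2.4.3.1 misname the role of status.

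The power figures show direction and rough size only. They rest on assumed ρ and p, bivariate normality and n = 80. The per-protocol, binding-positive IFN-K subset will be smaller, and 5.2.4.5.13 itself plans no test. They describe a continuous outcome such as signature change and do not carry over directly to BICLA or SRI-4. The primary conclusions are unaffected.

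**What to change.** In SAP 5.2.4.5.13, for IFN-K patients:

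- Add Spearman correlations with 95% CIs between Week 36 log NC50, and separately log binding titre, and change from Week 0 in gene signature, C3 and anti-dsDNA (2 × 3 = 6).
- Add the same between signature change and change in C3 and in anti-dsDNA (2).
- Add logistic regressions of BICLA and of SRI-4 on log NC50 and on signature change (2 × 2 = 4).
- State that all of these are exploratory, unadjusted for multiplicity, and non-causal because they involve post-randomisation variables.
- Cross-refer to the models in 5.2.4.2, 5.2.4.3.1 and 5.2.4.5.2, and keep the six present tables as supportive.

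In 5.2.4.2, 5.2.4.3.1 and the affected table titles, change the role of neutralizing status from dependent to explanatory variable.

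The cost is SAP wording, a little table programming and 6 + 2 + 4 = 12 further exploratory estimates, which is the one real downside. No new data are needed and there is no alpha consequence. Making the change before database lock and unblinding keeps the analyses prespecified.

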5.2.5 Safety analyses

Safety variables will be tabulated and presented for all patients included in the Safety population (SAF).

5.2.5.1 ***Extent of exposure and compliance***

Compliance (see section 9) with study treatment will be presented by treatment group on the FAS and the PP populations. Treatment compliance will then be analyzed as a numerical variable as well as a categorical variable (Statistical table 14.1.28, Listing 16.2.5.1).

Statistical Analysis Plan

Study Name: IFN-K-002

SAP version & date: v4, 18/Jun/2018

To analyze the extent of exposure the following variables will be summarized by treatment group for the SAF (Statistical table 14.3.1, Listing 16.2.5.2):

- Number of administrations received and cumulative dose
- Duration (number of days) between first IP application and last IP application.
- Presence of anti-IFN α neutralizing antibodies

All administration of study product data will be provided in Listing 16.2.5.3.

5.2.5.2 Adverse events

Adverse event tabulations:

Tabulation of adverse events will present for each cell the following information: number of patients with at least one occurrence of the event, corresponding percentage and number of events (if relevant).

The following tables will be produced for the Safety population as well as by treatment group:

The definition of TEAEs is described in section 4.2.1.

The following period will be defined:

- before first dose
- [1st dose; 2nd dose[
- [2nd dose; 3rd dose[
- [3rd dose; 4th dose[
- [4th dose; 5th dose[
- [5th dose; Week 36]
- [Last dose; Week 36/Early Termination] (for AE which cannot be classified in the previous periods due to dose not received or premature study termination)

Summary table of adverse events (Statistical Table 14.3.2):

- Any AE
- Any TEAE
- Any TEAE by period
- Any TEAE leading to study treatment temporarily discontinuation
- Any TEAE leading to study treatment permanent discontinuation
- Any TEAE of intensity severe or more
- Any TEAE considered related to the study treatment (possibly or probably related)
- Any SAE
- Any SAE by period
- Any Treatment Emergent SAE (TESAE)
- Any TESAE leading to study treatment temporarily discontinuation
- Any TESAE leading to study treatment permanent discontinuation
- Any TESAE considered related to the study treatment (possibly or probably related)
- Any TESAE of intensity severe or more

Statistical Analysis Plan

Study Name: IFN-K-002

SAP version & date: v4, 18/Jun/2018

- Death

Detailed Tables:

All tables listed below will be presented by period (except if otherwise specified):

- Solicited local reactions during a 7-day follow-up period after each study product administration by SOC and PT (Statistical Tables 14.3.3.1 to 14.3.3.6)
- Solicited local reactions during a 7-day follow-up period after each study product administration by SOC, PT and intensity (Statistical Tables 14.3.4.1 to 14.3.4.6)
- Solicited systemic reactions during a 7-day follow-up period after each study product administration by SOC and PT (Statistical Tables 14.3.5.1 to 14.3.5.6)
- Solicited systemic reactions during a 7-day follow-up period after each study product administration by SOC, PT and intensity (Statistical Tables 14.3.6.1 to 14.3.6.6)
- TEAEs by SOC and PT (Statistical Tables 14.3.7.1 to 14.3.7.6)
- TEAEs by SOC, PT and status of IFN α neutralizing antibodies (positive/negative) at time of event (only on patients IFN-K treated) (Statistical Tables 14.3.7.7 to 14.3.7.10)
- TEAEs by SOC, PT and relationship (Statistical Tables 14.3.8.1 to 14.3.8.6)
- TEAEs by SOC, PT and intensity (Statistical Tables 14.3.9.1 to 14.3.9.6)
- TEAEs leading to permanent study treatment discontinuation by SOC and PT (Statistical Table 14.3.10) (only throughout the study)
- SAEs by SOC and PT (Statistical Tables 14.3.11.1 to 14.3.11.7)
- SAEs by SOC, PT and status of IFN α neutralizing antibodies (positive/negative) at time of event (only on patients IFN-K treated) (Statistical Tables 14.3.11.8 to 14.3.11.11)
- SAEs by SOC, PT and relationship (Statistical Tables 14.3.12.1 to 14.3.12.7)
- SAEs by SOC, PT and intensity (Statistical Tables 14.3.13.1 to 14.3.13.7)
- SAEs leading to permanent study treatment discontinuation by SOC and PT (Statistical Table 14.3.14)

The following rules will be applied to analyze the occurrence of AE according to the status of IFN α neutralizing antibodies (positive/negative):

- For adverse event which occurred between dose 1 and dose 3 included, status of neutralizing capacity will not be assessed
- For adverse event which occurred between 3rd dose (excluded) and Visit 6 (included), status of neutralizing capacity at visit 6 will be used
- For adverse event which occurred between Visit 6 (excluded) and Visit 9 (included), status of neutralizing capacity at visit 9 will be used
- For adverse event which occurred between Visit 9 (excluded) and Visit 12 (included), status of neutralizing capacity at visit 12 will be used

Statistical Analysis Plan

Study Name: IFN-K-002

SAP version & date: v4, 18/Jun/2018

Statistical Analysis Plan

Study Name: IFN-K-002

SAP version & date: v4, 18/Jun/2018

Adverse events listings:

All adverse events (including solicited local and systemic reactions) recorded during the study will be presented in Listings. The following information (if available) will be included in the listings (non-exhaustive list):

- Patient identifier
- Age, Ethnic origin (see section 9 Derived data), gender, weight
- The adverse event (System organ class, preferred term, reported term)
- Start date, end date, duration, period
- Severity (e.g., mild, moderate, severe)
- Seriousness (serious/non-serious)
- Action taken
- Outcome
- Relatedness assessment

Listings will be provided for:

- Solicited local reactions during a 7-day follow-up period after each study product administration (Listing 16.2.7.1)
- Solicited systemic reactions during a 7-day follow-up period after each study product administration (Listing 16.2.7.2)
- All other adverse events (Listing 16.2.7.3)
- Death, other Serious Adverse Events and Other Significant Adverse Events (Listing 16.2.7.4). Other significant Adverse Events will include cancer and severe infection (not exhaustive list)

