10.6.3 Study Product Discontinuation

If any of these AEs or conditions occur during the study, the patient must not receive additional doses of study product but should be encouraged to continue other study procedures until Week 36. The patient must be followed until resolution of the event or condition:

- Bronchospasm or anaphylactic reaction following the administration of study product.
- Any confirmed or suspected immunosuppressive or immunodeficient condition.
- Medications leading to discontinuation of study product (list in Section 10.7.2).

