13.4 Safety Endpoints

- Occurrence, intensity and relationship of any solicited local and systemic AEs during a 7-day follow-up period (i.e. day of study product administration and 6 subsequent days) after each IFN-K or placebo dose
- Occurrence, intensity and relationship of unsolicited local and systemic AEs occurring throughout the study period
- Occurrence and relationship of all SAEs occurring throughout the study period
- Occurrence and intensity of solicited local reactions 1 hour post study product administration
- Occurrence and intensity of solicited systemic reactions 1 hour post study product administration
- Hematological and biochemical levels within or outside the normal ranges and percent change from baseline at each visit
- Occurrence, intensity and relationship of any abnormality in physical examination, vital signs, 12-lead ECG, clinical laboratory evaluations
- Rate and severity of viral infections

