14.3.3.4	Solicited local reactions during a 7-day follow-up period after each study product administration by SOC and PT - Period [4th dose; 5th dose[X			
14.3.3.5	Solicited local reactions during a 7-day follow-up period after each study product administration by SOC and PT - Period [5th dose; Week 36]		X			
14.3.3.6	Solicited local reactions during a 7-day follow-up period after each study product administration by SOC and PT - Period [Last dose;Week 36/Early Termination]		X			
14.3.4.1	Solicited local reactions during a 7-day follow-up period after each study product administration by SOC, PT and intensity - Period [1st dose; 2nd dose[X			
14.3.4.2	Solicited local reactions during a 7-day follow-up period after each study product administration by SOC, PT and intensity - Period [2nd dose; 3rd dose[X			

Statistical Analysis Plan

Study Name: IFN-K-002

SAP version & date: v4, 18/Jun/2018

Number	Title	Screened	SAF	FAS	PP	Other
14.3.4.3	Solicited local reactions during a 7-day follow-up period after each study product administration by SOC, PT and intensity - Period [3rd dose; 4th dose[X			
14.3.4.4	Solicited local reactions during a 7-day follow-up period after each study product administration by SOC, PT and intensity - Period [4th dose; 5th dose[X			
14.3.4.5	Solicited local reactions during a 7-day follow-up period after each study product administration by SOC, PT and intensity - Period [5th dose; Week 36]		X			
14.3.4.6	Solicited local reactions during a 7-day follow-up period after each study product administration by SOC, PT and intensity - Period [Last dose; Week 36/Early Termination]		X			
14.3.5.1	Solicited systemic reactions during a 7-day follow-up period after each study product administration by SOC and PT - Period [1st dose; 2nd dose[X			
14.3.5.2	Solicited systemic reactions during a 7-day follow-up period after each study product administration by SOC and PT - Period [2nd dose; 3rd dose[X			
14.3.5.3	Solicited systemic reactions during a 7-day follow-up period after each study product administration by SOC and PT - Period [3rd dose; 4th dose[X			
14.3.5.4	Solicited systemic reactions during a 7-day follow-up period after each study product administration by SOC and PT - Period [4th dose; 5th dose[X			
14.3.5.5	Solicited systemic reactions during a 7-day follow-up period after each study product administration by SOC and PT - Period [5th dose; Week 36]		X			

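### The SAP's adverse-event tables for doses 1 to 4 count only events in patients who went on to the next injection, so they understate reactions that ended dosing

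*SAP*

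**What the plan says.** SAP 5.2.5.2 defines the periods used to tabulate adverse events. After a pre-dose period come four dose periods, of which the first is "1st dose; 2nd dose". Each includes its own dose and is closed, exclusively, by the next one. The fifth dose period is "5th dose; Week 36", so it ends at a visit and not at an injection. A last period, "Last dose; Week 36/Early Termination", is kept "for AE which cannot be classified in the previous periods due to dose not received or premature study termination". The detailed tables are split by these periods unless stated otherwise.

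SAP 10.1 applies the last period to solicited reactions too. Table 14.3.3.6 is titled "Solicited local reactions during a 7-day follow-up period after each study product administration by SOC and PT - Period [Last dose;Week 36/Early Termination", and Tables 14.3.4.6, 14.3.5.6 and 14.3.6.6 do the same for local reactions by intensity, systemic reactions, and systemic reactions by intensity.

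The endpoint in Protocol 13.4 is "Occurrence, intensity and relationship of any solicited local and systemic AEs during a 7-day follow-up period" following each dose, and SAP 4.2.1 repeats the per-dose aim. Protocol 13.9.5 also announces adverse-event summaries according to how many doses were given.

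**The concern.** A solicited reaction occurs within 7 days of an injection, so it can always be tied to that injection. The SAP's periods tie it there only if the patient later receives the next dose. The table for dose k (k = 1 to 4) is therefore conditioned on something that happens after dose k, and that a reaction to dose k may prevent. Protocol 10.6.3 gives one direct route from reaction to stopping: "Bronchospasm or anaphylactic reaction following the administration of study product" bars further doses. Investigators and patients may also stop for other reactions.

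At stake is the per-dose reactogenicity profile. SAP 7.3 drops the planned 1-hour post-injection analysis, so the 7-day period tables are the only per-dose reactogenicity summary left. The pooled period also mixes the 240 mcg doses (1 to 3) with the 120 mcg dose 4, and no table splits it by dose number.

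**Working it through.** The documents give no figure for this rule, so there is none to reproduce. The check applies the rule to each dosing pattern and then sizes the effect under stated assumptions.

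**1. Where events go** (periods from SAP 5.2.5.2).

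| Doses received | Events after the last dose | Events after earlier doses |
|---|---|---|
| 1 | pooled last-dose period | none |
| 1, 2 | pooled last-dose period | period of dose 1 |
| 1 to 3 | pooled last-dose period | periods of doses 1, 2 |
| 1 to 4 | pooled last-dose period | periods of doses 1 to 3 |
| 1 to 5, reaches Week 36 | period of dose 5 | periods of doses 1 to 4 |
| 1 to 5, leaves before Week 36 | unclear: dose 5 or pooled period | periods of doses 1 to 4 |
| 1, 3, 4, 5 (dose 2 missed) | period of dose 5, if Week 36 is reached | after dose 1: not defined; after doses 3 and 4: their own periods |

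The sixth row is unclear because the rule also names premature study termination. The last row is possible because Protocol 11.3 lets a patient miss an injection and continue. In that patient no scheduled second dose closes the first period, yet dose 1 is not the last dose either.

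**2. Size within one arm.** Let r be the true proportion with a given reaction after dose 1, and s the share of those patients who receive no dose 2. The dose 1 table then shows

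- r(1 − s), if the denominator is the whole arm;
- r(1 − s)/(1 − rs), if it is the patients who continued and only reactors stop.

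SAP 5.2.5.2 says that cells hold patients, percentage and events, but states no denominator by period, so both are given. Both r and s are assumptions. In the planned arm of 89, r = 5% is 4.5 patients and r = 10% is 8.9.

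| r | s | Shown, whole arm | Shown, continuing patients |
|---|---|---|---|
| 5% | 0% | 5.0% | 5.0% |
| 5% | 25% | 3.75% | 3.80% |
| 5% | 50% | 2.5% | 2.56% |
| 5% | 75% | 1.25% | 1.30% |
| 5% | 100% | 0% | 0% |
| 10% | 0% | 10.0% | 10.0% |
| 10% | 25% | 7.5% | 7.69% |
| 10% | 50% | 5.0% | 5.26% |
| 10% | 75% | 2.5% | 2.70% |
| 10% | 100% | 0% | 0% |

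With the whole arm as denominator, the table loses exactly the fraction s of the true rate. Changing to the patients who continued hardly alters this.

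**3. Between arms.** With whole-arm denominators, the table removes r × s from each arm's rate. The displayed risk difference is the true difference minus (r₁s₁ − r₀s₀), so it is distorted only if r × s differs between arms. For example (assumed), with r = 10% in both arms and s = 50% in one and 25% in the other, the table shows 5.0% against 7.5%: an apparent gap of 2.5 points where there is none.

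**4. What the documents say about scale.** The only related figure is the planned 10% dropout: 160/0.90 = 177.8, rounded up to 178, so about 18 patients. This does not give s. Some of the 18 may leave after dose 5 or have no event, while patients who stop injections but stay in follow-up (Protocol 10.6.3) also feed the pooled period.

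**The case against.** The strongest reply is that nothing goes unreported. Every family of tables split by period has a last-dose table (for example 14.3.7.6, 14.3.8.6, 14.3.9.6 and 14.3.11.7). Table 14.3.2 counts treatment-emergent events overall. Tables 14.3.10 and 14.3.14 show, by arm, the events and serious events that led to permanent discontinuation. The listings carry start dates and period, and Listing 16.2.5.3 carries dosing, so the dose can be recovered. The tables are descriptive and no test depends on them. Both arms receive the same adjuvant. All of this stands, and a reader who inferred that the reactions vanish from the safety report would be wrong.

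Bronchospasm and anaphylaxis are also a weaker example than they look. They are not among the solicited reactions in Protocol 12.2.2, so their absence does not breach the per-dose solicited endpoint. If 10.6.3 is followed, such an event after doses 1 to 4 is missing from that dose's treatment-emergent event table, but it remains in 14.3.7.6 and belongs in 14.3.10.

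What the reply does not repair is the per-dose solicited summary. Table 14.3.10 covers the whole study and 14.3.14 is not split by dose. Table 14.3.2 has no breakdown by event term. The solicited families have no whole-study table, and patient counts cannot be added across periods because one patient may appear in several. Rebuilding the dose from listings is manual work, not a planned analysis.

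**Conclusion.** The point holds for the period tables of doses 1 to 4. As written, they count only events in patients who received the next injection, and so understate reactions that ended dosing. This conflicts with the stated aim of assessing solicited reactions after each dose. The relative loss equals the share of patients with the reaction who receive no further dose. The documents do not give that share, so the percentages above are illustrations, not estimates.

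Three stronger readings are tempting and not supported:

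- That overall safety reporting is incomplete. It is not, because the events appear elsewhere.
- That the comparison between arms is biased. That requires reaction-driven stopping to differ by arm, for which the documents give no evidence.
- That events before a missed middle dose are pooled in the same way. The SAP leaves that case undefined, which is an ambiguity.

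The last-dose period is labelled; what it lacks is the dose number. It may also take events after dose 5 in patients who leave before Week 36. Severity: should-fix. The primary efficacy analysis is untouched.

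**What to change.** In SAP 5.2.5.2, replace the period definitions with one rule. Assign each adverse event to the most recent injection actually received before onset, identified by its scheduled dose number. That period ends at the next injection received or, if there is none, at Week 36 or early termination. This also settles the missed-dose case and early departure after dose 5. State that the denominator for dose k is the patients who received dose k. Keep the last-dose tables as a supplement.

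One consequence needs a footnote. For unsolicited events, the dose 1 period would run up to 36 weeks in a patient who stops there but stays in follow-up, against 1 week in a patient who continues on schedule. Follow-up time should therefore be shown beside those tables. The 7-day solicited tables are not affected, because their window is fixed.

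The cost is a change of SAP wording and one derivation rule. The injection and event dates are already collected.
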